### **Intervention Description**

The oral education program in this study focused on (PD). It aimed to equip participants with the knowledge and skills to understand, manage, and prevent complications associated with periodontal conditions. The program was adapted from previous studies, with modifications made to suit the specific objectives of this research.

The educational content was based on the standard guidelines set by the World Health Organization. The oral education sessions lasted between 30 and 45 minutes and employed an interactive approach, incorporating various audio-visual aids such as dental forms,

models, charts, posters, and plaster models (Table 2). These materials were designed to engage participants actively, fostering a deeper understanding of oral health practices

**Table (2): Educational Sessions Program**

Session No.	Session Title	Duration & Group Size	Learning Objectives & Content	Teaching Methods	Instructional Tools	Evaluation Strategy
1	Anatomy & Physiology of the Oral Cavity and Clinical Presentation of Periodontal Disease	45–60 minutes, 30–35 participants	Objectives: Identify the major anatomical structures of the oral cavity; Explain the normal function of periodontal tissues Content: Overview of teeth, gingiva, periodontal ligament, alveolar bone; Signs and clinical presentation of periodontal disease (PD)	Interactive lecture & Q&A	Smartboard, photographs, PowerPoint, dental models	Prepare a brief report on a family member's oral condition
2	Prevention and Treatment of Periodontal Disease	45–60 minutes, 30–35 participants	Objectives: Describe primary preventive measures against PD; Compare non-surgical treatment options	Group discussion & live demonstration	Whiteboard & markers, photographs, PowerPoint	Compile a list of barriers to effective oral hygiene

			Content: Oral hygiene techniques: brushing, flossing, mouthwash; Professional measures: scaling, polishing, fluoride application		
3	Maintenance and Follow-Up of Preventive Measures	45–60 minutes, 30–35 participants	Objectives: Outline a maintenance schedule for periodontal health; Apply problem-solving strategies to common barriers  Content: Recall intervals and re-evaluation protocols; Strategies for overcoming patient-identified maintenance barriers	Brainstorming & group discussion	Photos, preventive devices (toothbrush, floss, mouthwash), posters, puzzles
4	Daily Preventive Practices	45–60 minutes, 30–35 participants	Objectives: Practice correct brushing and interproximal cleaning techniques;	Live demonstration under supervision	Whiteboard, PowerPoint, tooth models, preventive

			Reinforce daily oral-care routines	& mini-lecture	devices (brush, floss, mouthwash)
			Content: Live demonstrations of toothbrush and floss use; Hands-on practice with models and peer feedback		
5	Smoking and Its Harmful Effects on Periodontal Tissues	45–60 minutes, 30–35 participants	Objectives: Explain how tobacco smoking damages periodontal tissues; List short- and long-term oral health effects of smoking	Live demonstration on under supervision & lecture	Colorful PowerPoint slides with photos
			Content: Chemical effects of nicotine and tar; Epidemiology of PD in smokers vs. non-smokers		Compile a resource list on the oral-health impacts of smoking
6	Nutrition and Its Impact on Supportive Periodontal Tissues	45–60 minutes, 30–35 participants	Objectives: Analyze how different foods affect periodontal health; Recommend dietary adjustments to support	Group discussion & live demonstration on	Colorful PowerPoint slides with photos
					Prepare a list of dietary guidelines and resources on nutrition and oral health

periodontal tissues

Content: Role of  
sugars, acids, and  
antioxidants;

Nutritional  
guidelines and  
examples of tooth-  
friendly diets

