## **Study design**

A pre-test/post-test experimental design was utilised.

The study adopted an interactive educational approach to teach oral health self-care. This method actively engaged participants through two-way communication, practical demonstrations, and hands-on activities.

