**Table 1. Geographical Distribution and Proportional Sample Allocation of Schools in Nablus**

Area	Total Schools	Proportion of Total	Sample Size (Proportional)
East	27	41.5%	6
Nablus			
Central	25	38.5%	6
Nablus			
West	13	20.0%	3
Nablus			
Total	65	100%	15

To ensure proportional representation, schools were evenly selected from three geographical areas of Nablus (East, Central, and West), corresponding to the number of schools in each area (Table 1). The Epi Info program was used to calculate the sample size based on schools with 9th-grade classes (East = 27, Central = 25, West = 13). A total of 15 schools were selected: 6 from East Nablus, 6 from Central Nablus, and 3 from West Nablus. The final sample included 10 governmental schools and 5 private schools, ensuring proportional distribution across the city.

Schools were eligible for inclusion if they had 9th-grade classes, were feasible for participation in the study and data collection and implemented an appropriate consent

process for students and their parents. According to the educational directorate's records for 2024, Nablus City had 2832 9th-grade students in governmental schools (males = 1360, females = 1472) and 737 students in private schools (males = 434, females = 303).

The G\*Power program was used to estimate the required sample size for the study, following the guidelines of Kang (2015, 2020). The effect size was set at  $dz = 0.5$ , with an alpha error probability ( $\alpha$ ) of 0.05 and a study power of 90% ( $1 - \beta$ ).

Based on these calculations, 536 students from intervention schools and 410 students from control schools were required to obtain accurate and meaningful data.

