### **Data Collection Processes**

The Al-Quds Committee for Ethical Considerations approved this study (REF.13/24). Consent forms were distributed to students, and their approval was sought before data collection began.

The researcher trained five dentists to conduct interviews and dental examinations, ensuring the data collection process was standardised and calibrated. Training sessions for the data collectors were held every 15 days throughout the research period to maintain consistency and accuracy in data collection.

During the baseline phase, all participants were provided with a comprehensive explanation of the study. Baseline data were collected in March 2024. The selected participants were randomly divided into intervention and control groups, ensuring that both groups were matched by age and gender. The control group received one oral educational session, while the intervention group participated in six sessions. The educational sessions were held every 10 days over two months.

After two months of interactive education, participants were re-examined and interviewed. Follow-up data were collected in the same schools using the same dental examination measures and questionnaires used during the baseline phase.

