Test to use: Paired t-test, as the data is normally distributed.

B. Between-Group Analysis (Post-intervention comparison):

Purpose: To compare the post-intervention CPITN scores between the intervention and control groups.

Test to use: Independent T-test as the data is normally distributed

Note: The two groups were examined for their differences in baseline measurement.

2. Can interactive educational sessions reduce **S-Oral hygiene index scores** among 9th-grade students in Nablus City within two months?

1. Data Type and Variables

Dependent Variable: Simplified Oral Hygiene Index (S-OHI) score → Continuous quantitative variable

Independent Variable: Group type (Intervention vs. Control) → Binary categorical variable

Time Points: Pre-intervention (baseline)

Post-intervention (after two months) → true experimental design

2. Statistical Design

Since there are two time points and two groups, the analysis includes:

A. Within-Group Analysis (Intervention group only):

Purpose: To assess whether there is a significant improvement (reduction) in S-OHI scores after the interactive educational sessions.

Test to use: *Paired t-test*, as the data is normally distributed.

B. Between-Group Analysis (Post-intervention comparison):

Purpose: To compare the post-intervention S-OHI scores between the intervention and control groups.

Test to use: *Independent t-test*, as the data is normally distributed

3. Will oral hygiene practices, smoking habits, and dietary habits improve among 9th-grade students after interactive educational sessions are applied in Nablus City?

Questionnaire responses related to oral hygiene practices, dietary habits, and smoking behaviour were **recoded** into scale variables to facilitate the computation of mean scores pre-and post-intervention. Correct answers reflecting preventive behaviours, in line with American Dental Association (2023) guidelines, were assigned the highest scores, while incorrect responses received the lowest scores, for example:

- "Do you clean your teeth?": Yes = 1, No = 0
- "How often do you clean your teeth?": Once/day = 1, Twice/day = 2, Three times/day = 3
- "How long does it take to clean your teeth?": One minute = 1, Two minutes = 2, More than two minutes = 3, Don't know = 0
- "Brushing technique": Scrubbing = 1, Bass = 2, Modified Bass = 3
- "Toothbrush type": Hard bristle = 1, Soft bristle = 2, Medium bristle = 3

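### The intervention is taught in groups of 30–35, but the planned t-tests treat students as independent; if outcomes correlate within group, the CPITN and S-OHI intervals are too narrow even under individual randomisation

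*Protocol*

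**What the plan says.** **Delivery.** Protocol Table 2 lists "45–60 minutes, 30–35 participants" for each of the six sessions. The Study design section describes the teaching as interactive: "This method actively engaged participants through two-way communication, practical demonstrations, and hands-on activities". The Data Collection Processes section gives the contrast between arms: "The control group received one oral educational session, while the intervention group participated in six sessions". The group size for the control session is not stated.

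**Allocation.** The same section says "The selected participants were randomly divided into intervention and control groups". The text under Table 1 says "536 students from intervention schools and 410 students from control schools were required", which reads as allocation of schools, and also "A total of 15 schools were selected".

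**Analysis.** For CPITN (SAP Question 1, between-group analysis) the SAP says "Test to use: Independent T-test as the data is normally distributed". For S-OHI (Question 2) the purpose is "To compare the post-intervention S-OHI scores between the intervention and control groups", again by independent t-test. Question 3 treats the three behaviour scores in the same way. Within-arm change is tested with paired t-tests, in both arms for CPITN and in the intervention arm only for the other outcomes. The SAP promises 95% intervals for all primary outcomes.

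Neither document mentions a design effect, mixed model, GEE, cluster-robust errors, or any adjustment for session group, class or school. The coefficients of 0.83 and 0.98 under Clinical Screening measure examiner reliability, not correlation between students.

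**The concern.** A t-test assumes that each student contributes independent information. Students taught together share peers, questions and discussion, so their post-programme scores may resemble each other more than those of students in different groups. Individual randomisation does not prevent this, because the correlation arises after allocation, through delivery. With six sessions in one arm and one in the other, it may also differ by arm.

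If the correlation exists, the t-test understates the standard error of the between-arm difference in both primary indices. Nominal 95% intervals then cover less than 95%, and p < 0.05 is reached too often when the average effect is zero. The paired test in the intervention arm is affected more, because no unclustered arm dilutes the error. A school term common to both arms would not cure this if students were split within schools, because the extra variation arises among session groups inside the intervention arm.

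**Working it through.** **Inputs from the documents.** 536 intervention and 410 control students (text under Table 1); groups of 30–35 (Table 2); 15 schools; 95% intervals and p < 0.05 (SAP).

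**The plan's own figure.** 536 and 410 do not reproduce from the stated inputs. A paired effect dz = 0.5 at 90% power and two-sided alpha 0.05 needs 44 pairs. An independent t-test with d = 0.5 needs about 86 per arm. The two numbers are used here only as the planned arm sizes.

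**Assumptions.** Between-student ICC (ρ) of 0.01–0.10; each student stays in one group of size m for all six sessions. This gives 536/35 = 15.3 to 536/30 = 17.9, so about 15–18 groups.

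**Formulas.**
- Design effect: DE = 1 + (m − 1)ρ.
- SE ratio, clustering in the intervention arm only: f = √[(DE/536 + 1/410) / (1/536 + 1/410)].
- SE ratio, same clustering in both arms, or the within-arm paired test if ρ applies to change scores: f = √DE.
- False-positive rate for an average effect of zero: 2Φ(−1.96/f). Coverage of the nominal 95% interval is one minus this.

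**Worked case.** With m = 33.5 (16 groups) and ρ = 0.05, DE = 1 + 32.5 × 0.05 = 2.625. Then f = √[(2.625/536 + 1/410) / (1/536 + 1/410)] = 1.305, the false-positive rate is 13.3% and coverage is 86.7%. With both arms clustered, f = √2.625 = 1.62 and the rate is 22.6%.

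**Range (m = 30 to m = 35).**

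| ρ | DE | f, one arm | False positives, one arm | f, both arms or paired | False positives |
|---|---|---|---|---|---|
| 0.01 | 1.29–1.34 | 1.06–1.07 | 6.5–6.7% | 1.14–1.16 | 8.4–9.0% |
| 0.02 | 1.58–1.68 | 1.12–1.14 | 8.0–8.5% | 1.26–1.30 | 11.9–13.1% |
| 0.05 | 2.45–2.70 | 1.28–1.32 | 12.5–13.7% | 1.57–1.64 | 21.1–23.3% |
| 0.10 | 3.90–4.40 | 1.50–1.57 | 19.2–21.3% | 1.98–2.10 | 32.1–35.0% |

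**Simulation check.** With 17 intervention groups and 410 independent controls, the plain t-test rejected 5.1% at ρ = 0, 6.5% at 0.01, 8.0% at 0.02, 12.8% at 0.05 and 19.6% at 0.10, in line with the formula.

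**If schools were allocated.** The mean is 946/15 = 63.07 students per school. DE = 1 + 62.07ρ runs from 1.62 to 7.21 for ρ = 0.01–0.10, an SE ratio of 1.27 to 2.68 and a false-positive rate of 12–47%. I simulated 8 against 7 schools with two session groups in each, so that the correlation lies at school level. A Welch test on session-group means rejected about 8%, 13% and 15% at school ICC 0.01, 0.05 and 0.10. A test on school means held about 5%.

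**The case against.** **Nothing in the documents shows that the correlation exists or how large it is.** This stands. The ICC is assumed, and at 0.01 the one-arm rate is under 7%, close to nominal. The documents do not say that groups stayed fixed over six sessions; changing membership would weaken the effect. Nor do they say who taught. If one educator taught every group, a shared educator adds no variation between groups.

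**Table 2 is not uniformly interactive.** This also stands. Brainstorming appears only in session 3 and peer feedback only in session 4. Session 1 is an interactive lecture with questions, and session 5 combines demonstration with lecture.

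**If the programme affects nobody, group teaching induces no correlation.** Correct under individual randomisation. The error rates above refer to group-specific effects that average to zero. Interval coverage does not need that special case: the intervals are too narrow at any average effect if groups vary.

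**Under individual randomisation within schools, variation between schools shared by both arms could partly offset the inflation.** It could. The plan would still misstate its uncertainty, and the model would need a school term as well.

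**If schools were allocated, school is the dominant cluster.** Agreed. A school-level analysis would then absorb session-group variation, and adjusting for session group alone would not be enough.

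**Stronger readings that the documents do not support.** A reader might infer that the intervals are certainly too narrow by a known amount; without an ICC they are not. A reader might also infer that a session-group analysis holds 5% in every case; it does not if schools were allocated. Finally, a reader might conclude from dz = 0.5 that the adjustment costs no power for the planned effect. That figure is a paired effect size, and the documents state no planned between-arm effect.

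**Conclusion.** The concern holds in conditional form. The plan teaches the intervention in groups and analyses students as independent, so any positive within-group correlation makes the stated intervals and p-values too optimistic, whichever unit was allocated. With fixed groups of 30–35, clustering in the intervention arm only and an assumed ICC of 0.01–0.10, the standard error is understated by a factor of about 1.06–1.57 and the false-positive rate for an average effect of zero is about 7–21%. With equal clustering in both arms the rate is about 8–35%. The direction follows from the design for any positive ICC; the size rests on the assumed ICC and on stable group membership. The unit of allocation is unresolved in the protocol and decides which cluster terms are needed. The SAP should be changed on this point. Confidence in the size is moderate at best.

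**What to change.** 1. **State the unit of allocation.** Reconcile the Data Collection Processes section (participants divided at random) with the text under Table 1 (intervention schools and control schools).

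2. **In SAP Questions 1–3, replace the independent t-tests with a mixed model adjusted for the baseline score.**
   - *If students were randomised within schools:* include a school effect and a random session-group (or class) effect in the intervention arm, and in the control arm too if its session was given in groups. Use arm-specific residual variances and Satterthwaite or Kenward-Roger degrees of freedom.
   - *If schools were allocated:* include a random school effect with session group nested in it, and small-sample degrees of freedom based on the 15 schools; or compare school means. Session-group adjustment alone is then not sufficient.

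3. **Base within-arm change intervals on the same clusters, and report the estimated ICC.** State whether group membership was fixed across the six sessions; if it was not, say how a student is assigned to a group for analysis.

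**Cost.** SAP wording, extra model terms and a session-group, class or school identifier in the data file. No more students or procedures are needed. The documents do not say that session-group attendance was recorded; if it cannot be recovered, class is the natural substitute. Intervals will be wider: at ICC 0.05 the standard error is about 1.3 times the t-test value with ungrouped controls, about 1.6 times if both arms are grouped, and more if schools were allocated. Small-sample degrees of freedom add a little to this.

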Statistical Analysis Plan (SAP)

Official Title: Effectiveness of an Interactive School-Based Oral Health Education Program in Reducing Periodontal Disease Among Palestinian Adolescents: A Double-Blind Intervention Study

NCT Number:

Document Date: March 1, 2024

Sponsor: Al-Quds University

Overview

This Statistical Analysis Plan outlines the statistical methods and procedures used to analyse data for the intervention study assessing the effect of a school-based oral health education program on periodontal conditions and related behaviours among 9th-grade students in Nablus City, Palestine.

Study Objectives

- Primary: To evaluate the effectiveness of the intervention on CPITN and S-OHI scores.
- Secondary: To assess changes in oral hygiene practices, dietary habits, and smoking behaviours.

Data Preparation and Management

Data were entered into IBM SPSS Statistics version 25.0.

All data were reviewed for completeness and consistency prior to analysis.

Normality testing was conducted using Shapiro-Wilk tests.

Missing data was minimal and handled by complete case analysis.

Statistical Analyses

Descriptive statistics will be used to summarise baseline characteristics by group (mean \pm SD, frequencies, percentages).

- Paired t-tests will be used to assess within-group differences from baseline to post-intervention.
- Independent t-tests were used to compare mean differences between the intervention and control groups.
- Statistical significance was set at $p < 0.05$.
- Confidence intervals were calculated at the 95% level for all primary outcomes.

Study Questions VS Analysis Plan

1. Can interactive educational sessions reduce **Community Periodontal Diseases Index** scores among 9th-grade students in Nablus City for two months?

1. Data Type and Variables

Dependent Variable: Community Periodontal Index for Treatment Needs (CPITN) **score** → Continuous quantitative variable

Independent Variable: Group type (Intervention vs. Control) → Binary categorical variable

Time Points: Pre-intervention (baseline)

Post-intervention (after two months) → true experimental design (pre-post measurements)

2. Statistical Design

Since there are two time points and two groups, the analysis includes:

A. Within-Group Analysis (Intervention group and control group):

Purpose: To assess whether there is a significant reduction in CPITN scores after the interactive educational sessions within the two groups themselves.

Test to use: Paired t-test, as the data is normally distributed.

B. Between-Group Analysis (Post-intervention comparison):

Purpose: To compare the post-intervention CPITN scores between the intervention and control groups.

Test to use: Independent T-test as the data is normally distributed

Note: The two groups were examined for their differences in baseline measurement.

2. Can interactive educational sessions reduce **S-Oral hygiene index scores** among 9th-grade students in Nablus City within two months?

1. Data Type and Variables

Dependent Variable: Simplified Oral Hygiene Index (S-OHI) score → Continuous quantitative variable

Independent Variable: Group type (Intervention vs. Control) → Binary categorical variable

Time Points: Pre-intervention (baseline)

Post-intervention (after two months) → true experimental design

2. Statistical Design

Since there are two time points and two groups, the analysis includes:

A. Within-Group Analysis (Intervention group only):

Purpose: To assess whether there is a significant improvement (reduction) in S-OHI scores after the interactive educational sessions.

Test to use: *Paired t-test*, as the data is normally distributed.

B. Between-Group Analysis (Post-intervention comparison):

Purpose: To compare the post-intervention S-OHI scores between the intervention and control groups.

Test to use: *Independent t-test*, as the data is normally distributed

3. Will oral hygiene practices, smoking habits, and dietary habits improve among 9th-grade students after interactive educational sessions are applied in Nablus City?

Questionnaire responses related to oral hygiene practices, dietary habits, and smoking behaviour were **recoded** into scale variables to facilitate the computation of mean scores pre-and post-intervention. Correct answers reflecting preventive behaviours, in line with American Dental Association (2023) guidelines, were assigned the highest scores, while incorrect responses received the lowest scores, for example:

- "Do you clean your teeth?": Yes = 1, No = 0
- "How often do you clean your teeth?": Once/day = 1, Twice/day = 2, Three times/day = 3
- "How long does it take to clean your teeth?": One minute = 1, Two minutes = 2, More than two minutes = 3, Don't know = 0
- "Brushing technique": Scrubbing = 1, Bass = 2, Modified Bass = 3
- "Toothbrush type": Hard bristle = 1, Soft bristle = 2, Medium bristle = 3

"Toothbrush replacement frequency": Every three months = 1, Two months = 2, Monthly = 3

Additional coding schemes are provided at the end of this document. The overall mean differences in oral hygiene practices, dietary habits, and smoking behaviour scores were then compared between groups using independent sample t-tests, with sub-analyses conducted for each behavioural domain separately. Statistical significance was set at $p < 0.05$.

1. Data Type and Variables

Dependent Variables (Behavioural Scores):

- **Oral hygiene practices score** → Continuous quantitative
- **Smoking habits score** → Continuous quantitative
- **Dietary habits score** → Continuous quantitative

Independent Variable: Group type (Intervention vs. Control) → Binary categorical

Time Points: Pre-intervention (baseline)

Post-intervention (after two months) → True experiment design (pre-post)

2. Statistical Design

Since the question involves **multiple behaviours** and **two time points**, the analysis will be conducted separately for each behavioural domain:

A. Within-Group Analysis (Intervention Group Only)

- **Purpose:** To evaluate if there was a significant improvement in each behaviour **after the intervention**.
- **Test to use:** Paired t-test for:
 - Oral hygiene practices score

- Dietary habits score
- Smoking habits score

(Assumes normal distribution)

B. Between-Group Analysis (Post-Intervention Comparison)

- **Purpose:** To compare post-intervention behavioural scores between intervention and control groups.
- **Test to use:**
 - **Independent t-test** for:
 - Oral hygiene practices
 - Dietary habits
 - Smoking behavior

(Assumes normal distribution)

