### **Clinical Screening**

In this study, the Community Periodontal Index for Treatment Needs (CPITN) was used to assess the prevalence of periodontal disease (PD) among 9th-grade students before and after the intervention. For adolescents, CPITN scores 0, 1, and 2 are used to assess gingivitis:

- Score 0: Healthy gingiva
- Score 1: Gingival bleeding observed after gentle probing
- Score 2: Presence of supra or sub-gingival calculus

For adults, CPITN includes the following scores for periodontitis:

- Score 3: Pathological pockets measuring 4 to 5.99 mm deep

Score 4: Pathological pockets measuring 6 mm or deeper

Each sextant of the mouth examined was assigned a code number, with the index teeth representing each sextant: 16, 11, 26, 36, 31, and 46 (22).

The Oral Hygiene Index-Simplified (OHI-S) was used to determine the oral hygiene status of the subjects. This index consists of two components: debris and calculus, each with a possible score range of 0 to 3. The amounts of calculus and debris were assessed by examining the facial surfaces of teeth numbers 11, 16, 26, and 31 and the lingual surfaces of teeth 36 and 46. The scores for calculus and debris were added together and divided by the number of examined surfaces to calculate the OHI-S score for each individual.

In the pilot phase of the study, the Interclass Correlation Coefficient (ICC) was calculated to assess the reliability of the clinical measurements. A total of 20 students were examined five times by five data collectors, resulting in ICC values of 0.83 for CPITN and 0.98 for OHI-S, indicating high reliability.

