### **Instrument Development**

The questionnaire utilised in this study was adapted from existing literature with modifications to align with the study's primary objective. The secondary aim was to evaluate the impact of the interactive oral education program on students' oral hygiene practices, dietary habits, and smoking behaviours two months after the implementation of the educational sessions. Initially, the questionnaire was developed in English and later translated into Arabic. To ensure accuracy, the translation was validated through a back-translation process from Arabic to English before being administered as a pre-test.

The questionnaire consisted of pretested standardised closed-ended questions that were assessed for face and content validity by three experts in the field. It was divided into five sections:

1. **Student Background:** This section included questions about the type of school (governmental or private) and the school system.
2. **Family Background:** The questions covered family size, parents' educational and occupational status, and the family's economic status.
3. **Oral Hygiene Practices:** This section addresses the frequency and technique of tooth brushing.
4. **Dietary Habits:** Questions focused on the frequency of breakfast consumption per week and the daily intake of nutritious versus non-nutritious foods.
5. **Smoking Behaviours:** This section assessed the frequency of cigarette and water pipe smoking and the number of cigarettes consumed.

The questionnaire's internal consistency was also evaluated using Cronbach's alpha, yielding a reliability coefficient of 0.967 for the 47 items tested.

The questionnaire was administered through direct interviews with individual students. All participants completed the questionnaire and underwent clinical examinations, resulting in

a 100% response rate. The questions in the questionnaire were designed to align with the topics covered in the educational program.

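### The SAP title claims a double-blind study, but students attend six sessions or one and neither document describes masking of anyone

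*SAP*

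**What the plan says.** The Official Title in the SAP ends with "A Double-Blind Intervention Study". In the text reviewed, which lacks the Protocol's opening page, this is the only reference to blinding. The Protocol, under Study design, says only: "A pre-test/post-test experimental design was utilised".

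The Protocol, under Data Collection Processes, describes the two arms: "The control group received one oral educational session, while the intervention group participated in six sessions". On timing it says: "The educational sessions were held every 10 days over two months". At baseline, "all participants were provided with a comprehensive explanation of the study".

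On assessment, the same section says: "The researcher trained five dentists to conduct interviews and dental examinations". It adds that the dentists were calibrated and retrained every 15 days, and that follow-up took place in the same schools as baseline. Under Instrument Development: "The questionnaire was administered through direct interviews with individual students". That section also says the questions were written to match the programme's topics. In the SAP's third study question, answers that reflect preventive behaviour receive the highest scores.

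The sample-size text, in the section on sampling, asks for 536 students from schools it calls intervention schools and 410 from schools it calls control schools.

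**The concern.** A reader who sees double-blind in a title assumes that neither the participants nor the assessors knew the arm, and sets aside reporting and assessment bias. Here those are the biases most likely to favour the intervention.

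All the behavioural outcomes are what students tell a dentist face to face, on topics that the intervention arm was taught at greater length. The primary outcomes, CPITN and OHI-S, depend on an examiner's judgement of bleeding, debris and calculus. If either source leans towards the intervention arm, the comparison of groups absorbs that lean as treatment effect, and no analysis in the SAP can separate the two. The label tells readers that this has been dealt with, and nothing in either document supports that.

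**Working it through.** **Step 1: the label against the described design, by role.**

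- *Students.* The arms differ openly, with six group classes or one, and Table 2 of the Protocol lists live demonstrations, supervised practice and take-home tasks. No sham or attention-matched programme is described. Everyone had the study explained at baseline, and nothing says that the hypothesis or the contrast between arms was withheld. Blinding of students is not credible.
- *Examiners and interviewers.* Five dentists were trained for both tasks. Neither document says that allocation was withheld from them, who taught the sessions, or how dentists were assigned to schools or arms. Follow-up was in the same schools, and the Protocol labels schools by arm, so the location alone could reveal the arm. Masking is neither described nor ruled out.
- *Data analyst.* Neither document mentions masking.

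Double-blind needs at least two masked roles. The design rules out the first in practice, and no other is documented.

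**Step 2: how small a bias would matter.** The plan states no figure on this, so there is nothing to reproduce. The inputs are 536 and 410 students (Protocol, sample-size text), a significance level of 0.05 (SAP, taken as two-sided because the side is not stated) and an independent t-test (SAP). The SD is that of whichever variable is tested, since the SAP refers both to mean differences and to post-intervention scores.

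- SE = √(1/536 + 1/410) = √(0.001866 + 0.002439) = 0.0656 SD
- Smallest observed difference with p < 0.05 = 1.96 × 0.0656 = 0.129 SD, about 0.13 SD

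**Step 3: effect of an assumed bias b when there is no true effect.** The documents give no size for b, so a range is shown. The probability of a significant result is 1 − Φ(1.96 − b/SE) + Φ(−1.96 − b/SE).

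| Assumed bias (SD) | Probability of p < 0.05 |
|---|---|
| 0 | 0.05 |
| 0.05 | 0.12 |
| 0.10 | 0.33 |
| 0.15 | 0.63 |
| 0.20 | 0.86 |

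For b = 0.10: b/SE = 0.10/0.0656 = 1.52, and 1 − Φ(1.96 − 1.52) ≈ 0.33. The last term is negligible.

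**Step 4: sensitivity to clustering.** The figures above treat students as independent, as the planned t-tests do. Suppose instead that the 15 schools are of equal size (946/15 = 63.1 students), the intraclass correlation is 0.01 to 0.05 (assumption), and the SE is corrected.

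- Design effect = 1 + 62.1 × 0.01 = 1.62, or 1 + 62.1 × 0.05 = 4.10
- SE = 0.0656 × √1.62 = 0.084 SD, or 0.0656 × √4.10 = 0.133 SD
- A bias of 0.10 SD then gives a significant result with probability 0.22 or 0.12

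The effect is weaker but still above 0.05.

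**The case against.** The best defence is that silence on examiner masking does not contradict it. The dentists may have been kept unaware of allocation, and then part of the label would be earned. This stands. A reader might infer that the examiners were unmasked, and the documents do not support that. They leave the question open, which is why the fix asks for the facts.

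Students may also have known their own number of sessions without knowing the other arm's, and controls did receive one session, so the contrast is one of dose. Both points are fair. Neither amounts to described blinding of participants.

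The dentists were calibrated and retrained, and the pilot gave good agreement, "resulting in ICC values of 0.83 for CPITN and 0.98 for OHI-S". This bears on consistency between examiners. It does not show freedom from a lean towards one arm.

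Two further readings are tempting and should not be adopted:

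- *The interview reveals the arm before the examination.* No order is fixed. Data Collection Processes mentions re-examination first and the interview second, and nothing says that the dentist who interviews a student also examines that student.
- *Differences between dentists are confounded with arm, as the CPITN coefficient of 0.83 suggests.* The documents do not say how dentists were spread over the arms. Uneven spread would be a separate fault, which masked dentists could share. The form of the coefficient is not given, and the value for OHI-S is 0.98.

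Finally, the 0.13 SD threshold follows from the sample size. It says how small a bias would matter, and is no evidence that one exists.

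**Conclusion.** The point holds. The title claims a property that the described design does not have for students and does not document for anyone else. The behavioural outcomes should be read as unblinded self-report, and assessor bias in CPITN and OHI-S cannot be excluded.

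The size rests on the stated 536 and 410 students and a two-sided 0.05 test: a shift of about 0.13 SD is enough for significance. The probabilities in the table also rest on assumed biases, and the clustered figures on assumed correlations and equal schools. A reader might go on to infer that bias did occur, or that a positive result would be spurious. The documents show neither.

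No planned test or estimate depends on the word, so the matter is one of labelling and disclosure. It should still be corrected, because it governs how far a positive result can be trusted.

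**What to change.** 1. Remove double-blind from the SAP title and wherever the title is reused.
2. State in both documents that students are not blinded and that the behavioural outcomes are unblinded self-report.
3. State what the five dentists actually knew. Write examiner-blind if they were kept unaware of allocation, and say how this was done. Otherwise write open-label.
4. Limit the conclusions accordingly, with separate remarks for the self-reported and the examiner-scored outcomes.
5. For any examinations still to be done, withhold the allocation list from the dentists, examine before interviewing, have each dentist examine students in both arms, and have none of them deliver sessions.

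Items 1 to 4 are changes of wording and can be made at any stage. Item 5 needs some scheduling effort but no extra staff or visits. It cannot help data already collected, and the Protocol's past tense suggests that follow-up may be complete. The other cost is a less favourable label.
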